Funder	National Institute of Diabetes and Digestive and Kidney Diseases (NIDDK)
Clinical Phase	NA
Study Rationale	Young adults (YAs) are underrepresented in behavioral health and weight loss interventions and express interest in flexible, highly tailored programs. Mobile interventions are a lower-burden, scalable approach to providing behavioral support. Just-in-time-adaptive interventions (JITAI) promise to deliver the “right” support at the “right” time using real-time data from smartphones and sensors. JITAI hold promise for promoting behavior changes needed for weight loss (eating, activity, and self-weighing); however, there is limited evidence for selecting treatment components and levels of adaptation that are needed for success. Results of this trial will be used to create an optimized JITAI for weight loss in young adults.
Study Objective(s)	
Primary
 
 • To build an optimized JITAI consisting of the set of intervention components that yield the greatest improvement in weight change among young adults at 6 months 
Secondary
 
 • To conduct mediation analyses to test the relationships between the intervention components and hypothesized proximal mediators (self-regulation, competence, relatedness, relevance, autonomy) and more distal behavioral mediators (dietary intake, physical activity, and daily self-weighing) • To conduct exploratory analyses of program engagement
Test Article(s) (If Applicable)	All participants will receive a core 6-month weight loss intervention that includes evidence-based lessons, behavioral skills training, and daily weighing.
Study Design	The AGILE (Adaptive Goals and Interventions for Lifestyle Enhancement) trial utilizes the Multiphase Optimization Strategy (MOST) framework and a 2^5 full factorial experimental trial to test the efficacy of 5 intervention components, each with two levels, on weight loss among 608 YAs recruited from around the United States. All participants will receive a core 6-month weight loss intervention that includes evidence-based lessons, behavioral skills training, and daily weighing. With the goal of determining if greater adaptation leads to greater weight loss, we will test standard versus adaptive options of 5 additional intervention components: 1) diet monitoring approach (standard vs. simplified), 2) adaptive physical activity goals (weekly vs. daily), 3) decision points for message timing (fixed vs. adaptive), 4) decision rules for message content (standard vs. adaptive), and 5) message choice (no vs. yes). Assessments will occur at baseline, 3 months, and 6 months.
Subject Population	
Inclusion Criteria
 
 1. Age 18-39 2. Body mass index (BMI) of 25-45 kg/m² 3. English speaking and writing

4. Own a smartphone with a data and text messaging plan
5. Willing to be randomized to any levels of the factors

Exclusion Criteria

1. Type 1 diabetes or currently receiving medical treatment for Type 2 diabetes.
2. Other health problems which may influence the ability to walk for physical activity or be associated with unintentional weight change, including cancer treatment within the past 5 years or tuberculosis.
3. Report a heart condition, chest pain during periods of activity or rest, or loss of consciousness on the Physical Activity Readiness Questionnaire (PAR-Q; items 1-4).
4. Lost 10 or more pounds (and kept it off) in the last 6 months.
5. Currently taking weight loss medications.
6. Report a past diagnosis of or receiving treatment for a DSM-IV-TR eating disorder (anorexia nervosa or bulimia nervosa).
7. Currently pregnant, pregnant within the past 6 months, or planning to become pregnant within the next 6 months.
8. Hospitalization for depression or other psychiatric disorder within the past 12 months. History of psychotic disorder or bipolar disorder.
9. Another member of the household is a participant or staff member on this trial.
10. Currently participating in a weight loss, nutrition or physical activity study or program or other study that would interfere with this study.

Number Of Subjects	608
Study Duration	Each subject's participation will last 6 months. The entire study is expected to last five years.
Study Phases	(1) Screening : screening for eligibility and obtaining consent and (2) Baseline assessment
Screening	(3) Intervention : study intervention/experimental treatment. (4) Follow-up assessment will
Study Treatment	occur at 3 and 6 months.
Follow-Up	
Efficacy Evaluations	Results of the optimization experiment will be used to determine which combination of components and component levels contribute most significantly to mean weight loss (primary) and achievement of 5% weight loss (secondary) at 6 months.
Pharmacokinetic Evaluations	NA
Safety Evaluations	All medical events and safety data will be assessed at assessment points or when interim events are reported by participants using a standard form used in our ongoing NIH funded trials.
Statistical And Analytic Plan	The primary outcome analysis will use mixed effects models to test for differences in weight by intervention components across time (baseline, 3, and 6 months). ²⁴ Effects will be modeled as component x time interactions with the 6-month outcome as the primary endpoint. All higher-order interactions between components will be modeled. Additional models will evaluate the likelihood of reaching 5% weight loss at 6 months.
DATA AND SAFETY MONITORING PLAN	Data safety management in this trial is intended to achieve 4 objectives: 1) to minimize the occurrence of adverse effects, especially those related to intervention; 2) to effectively

manage adverse events as they relate to the study; 3) to identify when the interventions should be suspended because of concerns for participant safety; and 4) to determine when interventions may be resumed after having been suspended. The Principal Investigator ([name]) will have primary responsibility for the safety of participants as it relates to the study protocol, which must be approved by the UNC IRB prior to study initiation. In addition, the North Carolina Translational and Clinical Sciences (TraCS) Institute Data Safety Monitoring Board (DSMB) is responsible for reviewing data from clinical trials approved by the UNC Biomedical IRB. Because the risks to subjects participating in this phase of this study are expected to be low, we do not anticipate the need for a formal Data Safety Monitoring Board. The research team will provide continuous monitoring of participant safety and periodic reporting to the IRB as required, including any Unanticipated Problems/Severe Adverse Events that may have occurred during the study. If risk or complexity is significant, the UNC Office of Human Research Ethics may require additional reporting or alternative data and safety monitoring. Data safety and monitoring activities continue until all participants have completed treatment and until all participants have been followed to the point at which study related adverse events would likely no longer be encountered.

BACKGROUND AND RATIONALE

1.1 Introduction

Obesity has reached epidemic proportions in the United States and is recognized as a major cause of morbidity and mortality. There is an increased risk of weight gain during young adulthood,¹⁻² and 40% of young adults (YAs) aged 20-39 years are living with obesity.³ Obesity in this age group is associated with increased risk of hypertension, hyperlipidemia, diabetes, and cancer.²⁻⁴ Despite these risks, YAs are underrepresented in behavioral weight loss programs⁵⁻⁷ and few evidence-based programs have been designed specifically for YAs.⁷⁻¹⁰

1.2 Name and Description of Investigational Intervention

The AGILE (Adaptive Goals and Interventions for Lifestyle Enhancement) trial is a 2⁵ full factorial experimental trial testing the efficacy of 5 intervention components (factors), each with two levels, to identify component levels that contribute to greater weight loss among YAs. To do so, we will randomize 608 YAs with overweight or obesity to receive one level of each of the 5 intervention components, in addition to a core mobile-delivered behavioral weight loss program.

1.3 Relevant Literature and Data

Almost all young adults in the United States own a smartphone (97%) and mobile phone ownership in this age group is widespread across all racial/ethnic, education, income, and residential groups.¹¹ Our formative work with YAs (n=137) with overweight or obesity indicates that at least 60% are interested in technology-delivered programs, and that YAs would like programs that are individualized, lower intensity, flexible, and minimize time burden.¹² Commonly cited barriers to weight management among YAs include not having enough motivation or time and not getting enough exercise.¹² Exclusively mobile treatments have produced weight losses of 1-6 kgs over 6 months,^{9,13-15} demonstrating that mobile-delivered programs have the potential to increase the access, reach, and impact of weight management.

To date, the most effective digital obesity interventions have relied on predetermined, fixed schedules of treatment contact, typically providing email counselor feedback once per week and/or text messages delivered on a pre-specified schedule to all participants.¹⁶ With the widespread use of smartphones and connected health devices that seamlessly collect daily participant health data, mobile programs are able to provide more tailored intervention messages, such as varying message content based on current or recent behavioral data (e.g., activity minutes so far that day at time of message; number of days a goal was met in the past week).¹⁷⁻¹⁹ The availability of participants' real-time digital health data allows for highly individualized intervention and real-time support while minimizing burden to the participant. Rather than relying on largely pre-determined messaging schedules that evaluate a limited number of variables, emerging research has focused on improving the ability to send the "right message" at the "right time." These interventions, called "just-in-time adaptive interventions," (JITAs) have the potential to improve upon outcomes by offering highly adaptive, personalized feedback on behavior when needed.²⁰ Examples of JITAs have included providing just-in-time skills support for reducing alcohol intake,²¹ in-the-moment messaging to disrupt sedentary behavior,²² and using data to predict dietary lapses and provide supportive interventions before they occur.²³ Despite widespread availability of digital health devices and the emerging use of JITAs, most JITAs to date have been short in duration (12 weeks or less) and have targeted single behaviors versus multiple. In turn, there remains limited theoretical, empirical, and practical evidence to inform interventions.²⁰

To improve weight, multiple daily behavioral targets are needed, including dietary intake, physical activity, and self-weighing. Thus, for weight loss, automated mobile interventions must be able to provide tailored, adaptive messaging that considers participants' behavioral contexts across all weight-related behaviors and sends the "right" message for the "right" behavior and at the "right" time. However, the level of tailoring provided in messaging exists along a continuum, and it is not yet known how much tailoring and adaptation is needed to be effective. Moreover, there are other components of automated interventions that could increase engagement or effectiveness, including adaptive goal setting and alternative methods of self-monitoring, but few studies have examined alternatives among YAs. We conducted a pilot 12-week remotely delivered JITAI that delivered up to 4 messages per day to young adults in a mobile behavioral weight loss program and found that participants viewed 68% of messages, and viewing messages was associated with increased likelihood of reaching daily behavioral goals.¹⁸ While this was promising, many questions remain about how adaptive and personalized a JITAI needs to be to be effective for weight loss in YAs.

1. STUDY OBJECTIVES

To address evidence gaps regarding JITAIs, the objective of this trial is to simultaneously test innovative or adaptive intervention components, compared to their standard counterparts, that are expected to increase weight loss among YAs. This is an optimization trial, conducted as part of the Multiphase Optimization Strategy (MOST) framework.²⁴ Guided by Self-Determination Theory (SDT),²⁵ the trial will test 5 components that are designed to promote positive changes in SDT constructs: 1) diet self-monitoring approach (standard vs. simplified), 2) adaptive physical activity goals (weekly vs. daily adaptive), 3) decision points for message timing (fixed vs. adaptive), 4) decision rules for message content (standard vs. adaptive), and 5) message choice (no vs. yes).

Aim 1: Build an optimized JITAI consisting of the set of intervention components (and component levels) that yield the greatest improvement in weight change among young adults at 6 months. We will use a highly efficient experimental design, powered to detect both main effects and all two-way interactions between components. Results of the optimization experiment will be used to determine which combination of components and component levels contribute significantly to mean weight loss at 6 months. The proportion achieving 5% weight loss is our second-level decision-making criterion in cases of equal weight losses.

Aim 2: Conduct mediation analyses to test the relationships between the intervention components and hypothesized mediators. Mediators to be tested include the proximal theoretical mediators of component effects (self-regulation, competence, relatedness, relevance, autonomy) and the more distal behavioral mediators (dietary intake, physical activity, and daily self-weighing).

Aim 3: Conduct moderation analyses. The primary moderator to be tested is intervention engagement including self-monitoring engagement (weighing frequency, diet monitoring, tracker wear) and app engagement (app views, lessons, feedback, intervention message views). Exploratory moderators include gender, race/ethnicity, and initial BMI status.

The active component levels determined from this study will be used to create an optimized just-in-time adaptive intervention that will be tested in a separate RCT to examine weight losses at 6 months with follow-up at 12 months. If the proposed aims are achieved, we will expand our understanding of ways to improve public health with just-in-time support that accounts for individual variability in lifestyle and environmental contexts. Our work advances the science of JITAI development—answering key questions about adaptation and tailoring—and is guided by a conceptual model, which will further understanding of how JITAI components and mobile interventions may operate via key theoretical mediators. Our study will be one of the first to systematically

optimize a fully automated mobile JITAI. These aims are critical initial steps for overcoming the challenge of providing and evaluating broad-reach public health interventions that are more precisely tailored to the specific characteristics of individuals.

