4. STATISTICAL CONSIDERATIONS

Sample Size and Power

We defined a 1-kg weight change as more than a minimal effect of any given component on overall weight loss. We estimated standard deviation based on a prior cell phone-delivered intervention for YAs that found a standard deviation of 6.9 kg for a weight change difference of 2.2 kg between groups;⁹ therefore, we conservatively estimated a standard deviation of 4 times our 1-kg weight change estimate. Assuming a type 1 error rate of 5% and a standard deviation of 4 kg, reaching 80% power would require 505 total participants. Assuming a 17% attrition rate at 6 months based on our previous studies with YAs and rounding up to a whole number per condition results in a total of 608 participants needed. Thus, each of the two levels of each component will have 304 randomly assigned participants, with 19 participants in each of the 32 conditions.

Statistical Analysis

Aim 1 Analysis. To test for differences in weight change across time by the five intervention components, we will use mixed effects models on an intention-to-treat data set, with effects modeled as component \times time interactions and the 6-month outcome as the primary endpoint. We will run separate models for (a) mean weight change and (b) the proportion of participants achieving 5% weight loss, the latter constituting a second-level decision-making criterion in cases where effects for mean weight change are equal. All higher-order interactions between components will also be modeled (e.g., adaptive physical activity goals \times message choice \times time interaction). The ability to test all higher-order interactions between intervention components, without reducing power, is a key advantage of the factorial experiment, as this is not possible in a traditional multi-component RCT. We will be using effect (-1,1) coding rather than dummy (0,1) coding, which keeps any covariances among main effects and interactions to a minimum. Once we have identified important effects in the initial set of models, we will establish parsimonious prediction models in which coefficients that do not contribute significantly to mean weight loss (or proportion achieving 5% weight loss) will be set to zero.

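### Does the Aim 1 claim of power for all two-way interactions fail for a component that works at only one level of its partner?

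*Combined protocol and SAP*

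**What the plan says.** Study Objectives, Aim 1, seeks "the set of intervention components (and component levels) that yield the greatest improvement in weight change among young adults at 6 months" and makes the power claim "We will use a highly efficient experimental design, powered to detect both main effects and all two-way interactions between components". Results are to be used to "determine which combination of components and component levels contribute significantly to mean weight loss at 6 months".

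Sample Size and Power, in Statistical Considerations, contains one calculation. The target is "We defined a 1-kg weight change as more than a minimal effect of any given component on overall weight loss", and "Assuming a type 1 error rate of 5% and a standard deviation of 4 kg, reaching 80% power would require 505 total participants". Allowing for 17% attrition, this becomes 608, or 19 in each of 32 conditions. No interaction size or pattern is given.

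The Aim 1 Analysis specifies the coding ("We will be using effect (-1,1) coding rather than dummy (0,1) coding") and models all higher-order interactions. It then forms a parsimonious prediction model in which "coefficients that do not contribute significantly to mean weight loss (or proportion achieving 5% weight loss) will be set to zero". Achieving 5% weight loss is the second criterion when effects on mean weight change are equal.

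**The concern.** The word powered has no size attached where interactions are concerned. Most readers think of an interaction as the difference between a component's effects at the two levels of its partner. On that scale a 1 kg interaction has far less than 80% power. The omission seems to matter because significance drives selection: a coefficient that misses the 5% level is zeroed. A component that works only alongside a partner has its effect split over two half-size terms, and both can be lost.

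The factors make some dependence plausible. Timing, content rules and message choice all act on the same messages, and part of message choice works through the action planning tool, whose availability differs between the two sets of decision rules. At stake would be a useful component left out of the optimized package. The later RCT tests a package built from the chosen levels, so it could not bring that component back.

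**Working it through.** **Inputs.** From Sample Size and Power: two-level components, effect 1 kg, SD 4 kg, 5% error rate, 80% power, 505 evaluable, 608 enrolled. From the Aim 1 Analysis: (-1,1) coding, with non-significant coefficients zeroed. Assumed here: a 6-month change score, near-equal cells, two-sided tests and no multiplicity adjustment.

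**The plan's own figure.** N = 4 × SD² × (1.96 + 0.8416)² / effect² = 4 × 16 × 7.849 / 1 = 502.3. With the t distribution, power first reaches 80% at 505 (0.8006). Then 505 / 0.83 = 608.4, and 19 × 32 = 608. Both figures reproduce, apart from trivial rounding.

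**Scale of the interaction.** Write the model as b1·A + b12·A·B, with A and B at ±1. The effect of A is 2(b1 + b12) at B = +1 and 2(b1 − b12) at B = −1.

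- The main effect is 2·b1 and the effect-coded interaction is 2·b12. Each has SE 2 × 4 / √505 = 0.356 kg.
- The difference between the two effects of A is 4·b12, with SE 4 × 4 / √505 = 0.712 kg.
- A 1 kg effect-coded interaction therefore has the same power as a 1 kg main effect. It corresponds to effects of A that differ by 2 kg.
- The difference detectable with 80% power is 2.80 × 0.712 = 2.0 kg with 505, or 1.8 kg with all 608.

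**The one-sided pattern.** Let A give 1 kg at one level of B and 0 at the other. Then b1 = b12 = 0.25, so both effects are 0.5 kg. The ratio 0.5 / 0.356 = 1.40 gives power of 0.29 for each. The estimates are uncorrelated in the balanced design, so both are missed with probability 0.71² ≈ 0.51. Simulating the full 32-term model with 505 of 608 evaluable gives 50.9%.

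**Range.** Chance that both terms are zeroed when A gives 1 kg at one partner level and e at the other (e is assumed):

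| e (kg) | 0 | 0.25 | 0.5 | 0.75 | 1.0 |
|---|---|---|---|---|---|
| 505, SD 4 | 51% | 48% | 40% | 29% | 19% |
| 608, SD 4 | 44% | 41% | 32% | 22% | 12.5% |
| 505, SD 6.9 | 76% | 75% | 72% | 67% | 60% |

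The last row uses the SD of the cited trial ("found a standard deviation of 6.9 kg for a weight change difference of 2.2 kg between groups"). There a uniform 1 kg effect is itself missed 60% of the time, so the row reflects the choice of SD rather than interactions.

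**Consequence for the package.** A simulation of the 2^5 model used 16 per cell, SD 4 kg, e = 0 and a partner with an average effect of 1 kg, both innovative levels reinforcing each other. The shortfall is the true weight loss forgone relative to the best package.

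| Selection | Shortfall (kg) |
|---|---|
| Zero non-significant terms, undecided component to standard level | 0.55 to 0.64 |
| Same, undecided level at random | 0.36 to 0.37 |
| Same, undecided component to adaptive level | 0.05 to 0.16 |
| Keep all main effects and two-way terms | 0.11 |
| Use unpruned main effects only | 0.08 |

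The ranges come from different ways of breaking the remaining ties. Three comparisons put them in context.

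- With two 1 kg components and no interaction, zeroing with a standard-level default already misses the pair about a third of the time, with a shortfall of about 0.34 to 0.37 kg.
- If the interaction has the opposite sign and the partner still averages 1 kg, the shortfall is 0.16 to 0.18 kg with zeroing and 0.06 kg when two-way terms are kept.
- With all five components additive at 1 kg, the shortfall is about 0.86 kg with zeroing, 0.53 kg keeping two-way terms, and 0.01 kg using unpruned main effects only.

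**The case for a change.** The strongest case for acting is that Aim 1 wants the best package, yet the rule for reaching it rests on significance tests whose power for interactions is never sized. Full retention lowers the 51% only to 44%. Keeping main effects and two-way terms regardless of significance would cost a sentence or two and no participants. In the reinforcing scenario it chooses the right pair in 90% of trials, against 52% with zeroing and a standard-level default.

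What stands is that the plan does not state the interaction size, and it does not name a level for a component on which neither the weight model nor the 5% criterion decides. The power figures are also right.

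The rest does not carry.

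- The 1 kg target is defined for a component's effect on overall weight loss. A component averaging 0.5 kg is half that target, and any design with 80% power at its target has about 29% at half of it.
- The 52% depends on a default the plan never sets. With the opposite default, zeroing matches or comes close to the alternative in the same scenario.
- Unpruned main effects alone do as well or better, so the gain comes from giving up testing and not from handling interactions.
- Giving up testing has a price. If nothing works, the package carries about 2.5 of 5 innovative levels, against about 0.7 with zeroing and a standard-level default. That 0.7 rests on the same assumed default; assigning undecided levels at random would also give 5 × 1/2 = 2.5.
- The mechanism in the plan points the other way. Adaptive decision rules require a lapse of at least 4 days before the planning tool is offered, against 2 days in standard, so that part of message choice is less available under adaptive rules. The like/dislike part works under both, which makes e = 0 an extreme. The opposite-sign loss is not always small: with a partner whose average effect is 0 it is 0.55 kg with zeroing against 0.21 kg. The result turns on assumptions that the documents cannot settle.

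**Conclusion.** The concern does not call for a change. The power statement is correct on the effect-coded scale that the plan specifies. At 505 evaluable and SD 4 kg, 80% power applies to an interaction in which a component's effect differs by about 2.0 kg between levels of another, while a 1 kg difference has about 29%. The analyst can read this from the coding and the sample-size paragraph.

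The unnamed default level is also a matter of detail. When both coefficients are zero, the predicted mean weight changes are equal and the 5% criterion can be read as applying. It may not separate the levels, since that model is pruned too, and the analyst must then settle the level when the package is assembled.

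Replacing selection by significance with selection by largest prediction is a trade-off between missing modest components and carrying inert ones. The plan's choice is defensible. The conclusion rests on the change-score approximation, near-balanced cells and SD 4 kg. Whether 4 kg is the right SD is a separate question.
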